8.5 Vital Signs

8.5.1 Variables

The following vital signs will be summarized.

- Weight

- Systolic blood pressure (mmHg)
- Diastolic blood pressure (mmHg)

8.5.2 Analysis

Subject incidence of clinically meaningful changes since baseline for weight and blood pressure will be presented as shown below:

- Proportion of subjects with weight loss $\geq 10\%$ after first dose
- Subjects with at least 2 post-baseline assessments and who got worse since baseline and met the following blood pressure criteria on 2 or more visits (need not be consecutive) after first dose (JNC criteria were modified to include single measurement per time point when triplicate assessments were unavailable; (Chobanian AV, 2003)):
 - Pre-hypertension: SBP 120-139 mmHg or DBP 80-89 mmHg
 - Stage 1: SBP 140-159 mmHg or DBP 90-99 mmHg
 - Stage 2: (SBP ≥ 160 mmHg and DBP <120) or DBP 100-119 mmHg
 - Stage 3: DBP ≥ 120 mmHg

Only results with assessment dates through the end of the safety observation period (see Section 4.6) will be considered for the summaries.

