6.6.2.1.5. Hypertension

[Table 12](#) provides treatment guidelines for hypertension deemed related to cabozantinib. Blood pressure should be monitored in a constant position visit to visit, either sitting or supine in a relaxed setting. Decisions to reduce or interrupt the dose of study treatment must be based on BP readings taken by a medical professional and must be confirmed with a second measurement at least 5 minutes following the first measurement.

Cabozantinib should be discontinued in subjects with hypertension with life threatening consequences (eg, malignant hypertension, transient or permanent neurologic deficit, hypertensive crisis) or when urgent intervention is indicated.

Table 12: Management of Hypertension^a Associated with Cabozantinib

Criteria for Dose Modifications	Treatment/Cabozantinib Dose Modification
> 150 mm Hg (systolic) ^a and < 160 mm Hg OR > 100 mm Hg (diastolic) and < 110 mm Hg	
 Optimize antihypertensive medications by adding new or additional antihypertensive medications and/or increase dose of existing medications. Reduce cabozantinib treatment by one dose level if optimal antihypertensive therapy (usually to include 3 agents) does not result in BP < 150 mm Hg systolic and < 100 mm Hg diastolic. If subject is symptomatic interrupt cabozantinib treatment and restart only if symptoms have resolved and BP is < 150 mm Hg systolic and < 90 mm Hg diastolic.
≥ 160 mm Hg (systolic) OR ≥ 110 mm Hg (diastolic)	
 Reduce cabozantinib by one dose level or interrupt cabozantinib treatment per investigator discretion. Treatment should be interrupted if upper limits of systolic BP (≥ 160 mm Hg) are sustained and not adequately manageable or if systolic BP is > 180 mm Hg or sustained diastolic BP > 110 mm Hg, or if subject is symptomatic. Add new or additional anti-hypertensive medications and/or increase dose of existing medications and monitor subject closely for hypotension. If optimized antihypertensive therapy (usually to include 3 agents) does not result in BP < 150 mm Hg systolic and < 100 mm Hg diastolic, cabozantinib treatment should be dose reduced further or interrupted. Re-start cabozantinib treatment at reduced dose and re-escalate only if BP falls to and is sustained at < 150 mm Hg systolic and < 100 mm Hg diastolic.

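### SAP 8.5.2 gives no 'or higher' rule and no highest-stage rule for blood pressure, so a subject with two hypertensive visits in different stages can be counted in no stage, and one reading can count in two rows.

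*SAP*

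**What the plan says.** SAP 8.5.2 introduces the table with "Subject incidence of clinically meaningful changes since baseline for weight and blood pressure will be presented as shown below". The blood pressure part is restricted to "Subjects with at least 2 post-baseline assessments and who got worse since baseline", and they must have "met the following blood pressure criteria on 2 or more visits (need not be consecutive) after first dose". Four rows follow:

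- "Pre-hypertension: SBP 120-139 mmHg or DBP 80-89 mmHg"
- "Stage 1: SBP 140-159 mmHg or DBP 90-99 mmHg"
- Stage 2: systolic pressure of at least 160 "mmHg and DBP <120) or DBP 100-119 mmHg"
- Stage 3: diastolic pressure of at least 120

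Pre-hypertension and Stage 1 are bounded above on both components. Stage 2 is bounded on diastolic pressure but open on systolic, and Stage 3 is open. The only exclusion between rows is the diastolic limit of 120 in the systolic part of Stage 2, which separates Stage 2 from Stage 3. The section does not say whether the two visits must meet the same row, whether a higher stage counts toward a lower one, or where to put a reading whose systolic and diastolic values point to different stages. Neither document settles this elsewhere.

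**The concern.** A table of sustained blood pressure elevation should include every subject with two hypertensive visits and should show how severe the elevation was. Bounded rows that must each be met twice do neither reliably. A subject whose two raised visits straddle a boundary may meet each row only once and drop out. The 'systolic or diastolic' form also lets one reading meet two rows, so the rows do not sort subjects by severity.

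Other SAP safety summaries avoid this by using a worst value: worst severity for adverse events (8.1), maximum post-baseline grade for laboratory tests (8.4.2) and worst value for ECOG status (8.6). Hypertension matters here: Protocol 1.2 cites Grade 3 or 4 hypertension in 16% of subjects on cabozantinib against 1.7% on placebo in the Phase 3 study after sorafenib. Two programmers could also produce different tables from the present text.

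**Working it through.** The plan gives no figure to reproduce. The check applies the four printed rows literally, each to be met on at least two visits.

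**1. Worked pairs of visits**

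| Visit A (rows met) | Visit B (rows met) | Row met twice |
|---|---|---|
| 150/95 (Stage 1) | 170/105 (Stage 2) | none |
| 170/110 (Stage 2) | 175/122 (Stage 3) | none |
| 150/75 (Stage 1) | 165/75 (Stage 2) | none |
| 150/95 (Stage 1) | 165/95 (Stages 1 and 2) | Stage 1 |
| 150/85 (Stage 1, pre-hypertension) | 165/85 (Stage 2, pre-hypertension) | pre-hypertension |

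The first three subjects are counted nowhere. The fourth is counted only because 165/95 also meets Stage 1 on its diastolic value. The fifth appears only as pre-hypertensive although both visits are hypertensive.

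**2. What is logically possible.** Take all integer readings with systolic 90-220, diastolic 50-140 and a difference of at least 10: 10,091 readings. This grid is unweighted and says nothing about patient frequencies.

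- Readings meeting two rows: 1,010 (Stages 1 and 2) + 965 (Stage 2 and pre-hypertension) + 400 (Stage 1 and pre-hypertension) + 365 (Stages 1 and 3) + 55 (Stage 3 and pre-hypertension) = 2,795. Of these, 1,010 + 365 = 1,375 meet two numbered stages. None meets Stages 2 and 3 together.
- Highest stage 1: 955 + 400 = 1,355 readings. Highest stage 2: 3,105 + 1,010 + 965 = 5,080.
- Pair one of each. They share Stage 1 in 1,010/5,080 = 19.9% of pairs, and only pre-hypertension in (400/1,355) × (965/5,080) = 5.6%. They share no row in the remaining 74.5%.

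So the gap is the usual result for a subject with exactly one visit of each kind, but not the invariable one.

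**3. Likely size.** The documents give no blood pressure distribution, so all inputs are assumptions: systolic mean 135 or 145, between-subject SD 10, within-subject SD 12; diastolic mean 82-90, between-subject SD 6, within-subject SD 8; correlation 0.6. The denominator is subjects with at least two visits at Stage 1 or above. The worsening condition is not applied, because the SAP does not define it.

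| Post-dose visits | In no numbered stage | In two or more of the four rows |
|---|---|---|
| 3 | 5-6% | 54-59% |
| 5 | 1-2% | over 90% |
| 8 | under 1% | over 90% |

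If pre-hypertension counts as a row, the share in no row at all is under 2% at 3 visits and about 0% at 5 or more. The last column includes subjects whose different visits fall in different rows, as well as single readings that meet two.

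**4. Which line is typical.** The protocol expects about 6 months of treatment on average, with vital signs every 3 weeks. Weeks 4, 7, 10, 13, 16, 19, 22 and 25 make 8 visits. The 3-visit line describes subjects who stop early.

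**The case against.** The strongest reply is that the SAP never says both visits must meet the same row. Its words can be read collectively, as any listed criterion on two visits, and it cites published criteria that may carry their own assignment rule. This stands to the extent that the row-by-row reading is the natural one, not an express requirement. The collective reading still does not say which row such a subject enters, and the cited source is not reproduced in the plan.

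A second reply is that the effect is small and confined to a descriptive table. That also stands. SAP section 8 plans no formal safety comparison of the experimental and control arms, hypertension adverse events are tabulated by CTCAE grade under SAP 8.1, and Protocol 9.6.3 provides for shifts from baseline in vital signs. Overlapping rows are not an error in themselves, since the SAP does not claim they are exclusive.

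A reader might infer more than the documents support:

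- **Undercounting specific to the cabozantinib arms.** Protocol Table 12 says, at 160 systolic or 110 diastolic and above, "Reduce cabozantinib by one dose level or interrupt cabozantinib treatment per investigator discretion", together with new or intensified antihypertensive treatment. One could argue that the next visit will then often be in a lower stage. Neither document gives data on this and the simulation does not model it. Protocol 6.6.2.3 also lists hypertension among the common reactions to sorafenib, so a difference between arms is not shown.
- **A loss of about 13% at 3 visits.** That figure comes from a systolic-only calculation, which removes the diastolic alternative printed in every row below Stage 3. Adding diastolic pressure brings it to about 6%.
- **Distortion of the 16% against 1.7%.** Those are adverse event incidences, which this rule does not touch.

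**Conclusion.** The point holds as a minor defect. Applied row by row, SAP 8.5.2 can leave a subject with two hypertensive visits in no stage, and it lets one reading count in two rows. It does not do so for every mixed pair, because overlap rescues some. The omission is about 6% of subjects with two or more hypertensive visits at 3 visits, 1-2% at 5 and under 1% at 8, so it mainly concerns subjects with few visits. Overlap of rows is more frequent and makes severity by arm hard to read. These percentages rest on assumed means, SDs and correlation; the worked pairs rest on the printed text alone. Efficacy analyses and type I error are unaffected, and no differential bias between arms is shown.

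**What to change.** Amend SAP 8.5.2 in two steps. First, assign each visit to one category, the higher of its systolic and diastolic stage. Second, report the number of subjects with at least two post-dose visits, not necessarily consecutive, at pre-hypertension or higher, Stage 1 or higher, Stage 2 or higher, and Stage 3. The same amendment can state what worsening from baseline means on this scale.

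Under this rule 150/95 with 170/105 counts as Stage 1 or higher, and 170/110 with 175/122 as Stage 2 or higher. No subject can leave a row, because two visits that meet a printed row are also two visits at that category or higher. The number of subjects shown as hypertensive becomes slightly higher. The pre-hypertension and Stage 1 rows also rise by construction, since they now include the higher stages, so the table should label them as cumulative.

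The cost is SAP wording and programming. No data collection, clinical rule or efficacy analysis changes.

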8.6 ECOG Performance Status

The ECOG performance status of the subject will be assessed during screening and at each scheduled safety assessment starting on W1D1. For the purpose of evaluating safety, ECOG will be summarized as shift from baseline tables for, at minimum, the worst value recorded after the initiation of study treatment. Only results with assessment dates through the end of the safety observation period (see Section 4.6) will be tabulated in summary tables.

Frequencies of ECOG worsening of $\geq +1$ and $+2$ change from baseline to worst value after first dose will also be summarized.

8.7 Electrocardiogram (ECG)

Only results with assessment dates through the end of the safety observation period (see Section 4.6) will be considered for summaries. The following categorical summaries will be presented per investigator:

- Number of subjects with triplicate average QTc > 500 ms or increase in triplicate average QTc from baseline of > 60 ms after first dose per investigator
 - number of subjects with triplicate average QTc > 500 ms after first dose per investigator
 - number of cases referred for independent review (ERT)
 - number of cases confirmed as QTc > 500 ms by ERT.
 - number of subjects with increase in triplicate average QTc from baseline of > 60 ms after first dose per investigator
- number of subjects with increase in triplicate average QTc from baseline of > 30 ms after first dose per investigator

For the above summaries, the most-recent average value from triplicate measurements taken before first dose will be used as baseline. If no triplicate measurements were taken before first dose, the most-recent single or duplicate value taken before first dose will be used as baseline. If > 3 measurements are taken for an assessment, all will be included in the average.

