5.8.4. Electrocardiograms

At screening and during the study, single ECG assessments will be performed with standard 12-lead ECG equipment according to standard procedures to determine QTcF. A QTcF \leq 480 ms per single ECG within 14 days before randomization is required to demonstrate eligibility for study treatment. If at any time after the first dose of treatment the single ECG shows a QTcF with an absolute value $>$ 500 ms or an increase from baseline of $>$ 60 ms, two additional ECGs at intervals of approximately 3 min must be performed within 30 min after the initial ECG, and the average of these three consecutive results for QTcF will be used as the value assessed (see [Section 6.6.2.1.15](#)).

ECGs will be performed at the time points indicated in [Appendix A](#).

Guidelines for management of corrected QT prolongation associated with cabozantinib and sorafenib are provided in [Sections 6.6.2.1.15](#) and [6.6.2.3](#), respectively.

Abnormalities in the ECG that lead to a change in subject management (eg, dose reduced or interrupted, treatment discontinued, requirement for additional medication or monitoring) or result in clinical signs and symptoms are considered clinically significant for the purposes of this study and will be deemed AEs. If values meet criteria defining them as serious, they must be reported as SAEs ([Section 8.2](#)).

The Fridericia formula is depicted below for calculation of the corrected QT interval (QTcF).

$$QTcF = \frac{QT}{RR^{1/3}}$$

QT = measured QT interval in milliseconds; RR = measured R to R interval (which can be derived from the heart rate as 60/heart rate)

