6.6.2.1.15. Corrected QT Prolongation

The effect of orally administered cabozantinib 140 mg qd on QTc interval was evaluated in a placebo-controlled study in subjects with MTC. A mean increase in QTcF of 10-15 ms was observed after 4 weeks after initiating cabozantinib treatment. A concentration-QTc relationship could not be definitively established. Changes in cardiac wave form morphology or new rhythms were not observed. No cabozantinib-treated subjects in this study had a QTcF > 500 ms. Review of the larger safety database (approximately 5000 subjects exposed to cabozantinib in clinical trials and in post-marketing experience) confirmed the absence of safety concerns associated with QT prolongation. There were no events of torsades de pointes reported.

Concomitant treatment with strong cytochrome P450 (CYP) 3A4 inhibitors, which may increase cabozantinib plasma concentrations, should be avoided.

If at any time on study there is an increase in QTcF to an absolute value > 500 ms or an increase of > 60 ms above baseline per ECG evaluation at the site, two additional ECGs must be performed with intervals not less than 3 min apart within 30 min after the initial ECG.

If the average QTcF from the three ECGs is > 500 ms or an increase of > 60 ms above baseline, the following actions must be taken:

- Interrupt cabozantinib treatment
- Immediately notify the Sponsor
- Hospitalize symptomatic subjects (eg, with palpitations, dizziness, syncope, orthostatic hypotension) or those with a significant ventricular arrhythmia on ECG for a thorough cardiology evaluation and management
- Consider cardiology consultation for asymptomatic subjects for evaluation and management
- Check electrolytes, especially magnesium, potassium and calcium; correct abnormalities as clinically indicated
- Send copies of ECGs to central ECG laboratory for independent read
- Check concomitant medications for any medication that may have contributed to QT prolongation, and if possible, discontinue these medications (<http://www.qtdrugs.org>)
- Repeat ECG triplicates hourly until the average QTcF is \leq 500 ms and the average increase is \leq 60 ms above baseline or a consulting cardiologist or appropriate expert determines that the frequency of ECGs may revert to the schedule in the protocol.

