9.6.3. Other Safety Endpoints

Changes or shifts from baseline in vital signs, ECOG performance status, and QTc interval will be summarized by treatment group.

The number of subjects experiencing dose reduction, interruption/delay, and/or discontinuation due to an AE will be provided.

Concomitant medications will be standardized using the World Health Organization drug dictionary and summarized by class and preferred term.

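### The SAP counts QTc rises above 30 ms from triplicate averages only, but post-dose triplicates follow only a single QTcF above 500 ms or a rise above 60 ms, so most 31-60 ms rises cannot be counted

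*SAP*

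**What the plan says.** Protocol 5.8.4 sets how ECGs are taken: "At screening and during the study, single ECG assessments will be performed". After first dose, a single QTcF above 500 ms, or more than 60 ms above baseline, has this consequence: "two additional ECGs at intervals of approximately 3 min must be performed within 30 min after the initial ECG". The three readings are then averaged. The same trigger appears in the QT management text for cabozantinib (protocol 6.6.2.1.15) and for sorafenib (6.6.2.3), so it covers every arm.

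SAP 8.7 defines its investigator-assessed post-dose QTc categories (above 500 ms, rise above 60 ms, rise above 30 ms) on the triplicate average. The last is the "number of subjects with increase in triplicate average QTc from baseline of > 30 ms after first dose per investigator". If no triplicate was taken before dosing, the SAP accepts the latest single or duplicate reading as baseline. It has no matching rule for post-dose readings.

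Protocol 9.6.3 commits to more: "Changes or shifts from baseline in vital signs, ECOG performance status, and QTc interval will be summarized by treatment group". It does not limit this to triplicates.

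**The concern.** The 30 ms row is the only QTc summary in SAP 8.7 aimed below the 60 ms alarm, yet it depends on a measurement that is taken only once the 60 ms or 500 ms alarm has sounded. A subject with a scheduled single QTcF 45 ms above baseline and an absolute value of 480 ms has a moderate rise on record but no triplicate, and does not appear in the table.

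That range matters because protocol 6.6.2.1.15 reports, for cabozantinib 140 mg in an earlier placebo-controlled study: "A mean increase in QTcF of 10-15 ms was observed after 4 weeks after initiating cabozantinib treatment". If the distribution shifts by about that much, the upper tail falls mainly in the 31-60 ms band, which this row is least able to show. A reader of the study report could take a small count as reassurance when it mainly reflects which subjects had three ECGs.

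**Working it through.** The plan states no figure for this point, so there is none to reproduce. The check has two parts.

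**1. Which 31-60 ms rises can be counted**

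- A rise of 60 ms or less meets the trigger only through the absolute limit, that is, when baseline + rise > 500 ms.
- At the top of the band this needs a baseline above 500 − 60 = 440 ms. For a 45 ms rise it needs a baseline above 500 − 45 = 455 ms. For a 31 ms rise it needs a baseline above 500 − 31 = 469 ms.
- Eligibility caps QTcF at 480 ms (protocol 4.3, exclusion criterion 13), so the window is a baseline between 440 and 480 ms.
- The only other way to enter the row without entering the 60 ms row is for a single reading to rise more than 60 ms and its triplicate average to fall back to 31-60 ms.

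Other triplicates in the protocol do not fill the gap. Those at screening (single QTcF above 480 ms) are pre-dose and affect baseline only. The hourly triplicates in 6.6.2.1.15 follow a triplicate average already over the limit. Clinically indicated extra ECGs need not be in triplicate.

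**2. How large the gap could be (illustrative)**

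Only the trigger, the 480 ms cap and the 10-15 ms shift come from the documents. Assumed inputs:

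- baseline QTcF mean 420, 430 or 440 ms, SD 20-25 ms, at most 480 ms;
- mean post-dose shift 5, 10 or 15 ms;
- between-subject SD of change 10 or 15 ms, and within-subject SD 8 or 12 ms;
- four post-dose single ECGs, with a triplicate only after the trigger.

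Of subjects whose largest single-ECG rise was 31-60 ms, the share with no triplicate was:

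| Baseline mean | Share with no triplicate |
|---|---|
| 420 ms | 97-99% |
| 430 ms | 91-96% |
| 440 ms | 85-94% |

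Across all scenarios, 11.5-45.8% of subjects had some single-ECG rise above 30 ms, and the SAP row counted 0.1-11.3%. It captured 1-25% of the subjects with such a rise.

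One middle scenario: baseline mean 430 ms, shift 10 ms, between-subject SD 10 ms, within-subject SD 12 ms. Here 33.4% had a single rise above 30 ms, the SAP row held 3.2% and the 60 ms row held 0.8%. Of those peaking at 31-60 ms, 94.5% had no triplicate.

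**The case against.** The strongest objection is that single-ECG counts are no gold standard. A reader might take the gap between single-ECG and triplicate-rule counts as the number of true cases missed. That is not supported. In a second model (between-subject SD 8 or 10 ms, single-ECG SD 9 or 12 ms at baseline and at each of four visits, shift 10 ms), 22-33% show at least one single rise above 30 ms. The share whose underlying change exceeds 30 ms is only 1 − Φ((30 − 10)/8) = 0.6% to 1 − Φ((30 − 10)/10) = 2.3%. With no shift at all, 6-16% still show a single rise above 30 ms. The triplicate-rule count in that model, 0.15-1.7% without the 500 ms trigger, is nearer in size to the underlying share, though not necessarily in the same subjects. This stands: the single-ECG percentages are not true incidence.

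It is also tempting to say that noise would affect all arms equally. It would not. Counts over any visit grow with the number of ECGs. With no shift, going from four to six visits raises the count from 6.4% to 8.3% (smaller SDs) or from 16.0% to 19.8% (larger SDs). The schedule (Weeks 4, 7, 10 and 13, then every 12 weeks, plus the first follow-up visit) gives about six post-dose ECGs over the expected six months of treatment, and longer-treated arms would have more. This stands and shapes the fix.

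Third, the stakes are limited. Protocol 6.6.2.1.15 also reports no QTcF above 500 ms in the 140 mg study and no QT safety concern in about 5000 exposed subjects, and the doses here are 40-60 mg. Safety comparisons are descriptive. ECG abnormalities that change management or cause symptoms are recorded as adverse events. The 60 ms and 500 ms rows match the trigger and mostly work. All of this limits the severity, but none of it lets a subject without a triplicate into the 30 ms row.

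**Conclusion.** The point holds as a mis-specified row in a descriptive safety table. The rule as written excludes any subject with a 31-60 ms rise, an absolute value of 500 ms or less and no triplicate, so the row falls short of protocol 9.6.3. That conclusion follows from the text alone. The 85-99% figure rests on assumed QTcF distributions and four post-dose visits, and should be read as an order of size.

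Three stronger readings do not hold:

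- That a subject with a 45 ms rise can never have a triplicate. Above a baseline of 455 ms the 500 ms trigger applies.
- That the row would stay near zero whatever the drugs do. Every confirmed rise above 60 ms enters it, as do triggered ECGs that average down to 31-60 ms, so a strongly QT-prolonging drug would raise it.
- That the gap is itself evidence of harm. Nothing in the documents shows that.

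**What to change.** In SAP 8.7, define the post-dose categories (rise above 30 ms, rise above 60 ms, value above 500 ms) on the scheduled single QTcF where no replicates exist, and otherwise on the mean of the replicates. Keep the triplicate-average rows as separate rows for confirmed cases above 60 ms and above 500 ms. Present single-ECG change from baseline by scheduled visit beside any worst-post-baseline count, so that a difference in the number of ECGs is not read as a drug effect. Name the correction as Fridericia, since the SAP says only QTc.

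The cost is a few sentences and some programming. The single values are already collected. SAP 8.5.2 makes the same allowance for blood pressure, accepting one measurement where triplicates are missing, and SAP 4.9 provides the revision and addendum route. The price is noisier counts that rise with time on treatment, which the by-visit table addresses. ECG procedures and management rules are untouched.
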